5.7.4 Quality of life

It will be assessed using the QLQ-C30 (version 3) questionnaire for cancer and the FACT-HEP questionnaire specific to HCC.

Internal validation of the 30-item QLQ-C30 questionnaire identified 15 dimensions and calculated 15 scores: 5 functional ability scores (physical ability, ability to work or perform any household task, cognitive ability, emotional state, social state), a global quality of life score, a financial problems score, and 8 symptom scores (fatigue, nausea/vomiting, pain, dyspnea, sleep disturbance, loss of appetite, constipation, diarrhea).

The FACT-HEP (version 4) is composed of the 27 items of the FACT-G evaluating 4 dimensions (physical, social and family, emotional, functional) and 18 specific items (HepCS) allowing to evaluate the specific symptoms of HCC and the side effects of its management. Three scores will be calculated: the FACT-Hep TOI, taking into account the physical, functional, and specific symptoms of HCC; the FACT-G Total score, taking into account the physical, functional, emotional, social, and family dimensions; and the FACT-Hep Total score, taking into account all dimensions.

These different scores will be described at inclusion and during follow-up.

For the QLQ-C30 Global Health, Physical Ability, Cognitive Ability, and Fatigue scores, and the FACT-Hep TOI, FACT-G Total score, and FACT-Hep Total score, longitudinal progression will be studied, with the percentage of symptomatic progression defined as the percentage of patients who had a score decrease of at least 5 points from inclusion without subsequent improvement (Osoba, 1998). Patients lost to follow-up without a decrease in score of at least 5 points from inclusion will be considered without symptomatic progression. For the overall health score, FACT-Hep TOI, FACT-G Total score, and FACT-Hep Total score, time to definite deterioration, defined as the time interval between the date of randomization and the date of a score decrease of more than 5 points (from the inclusion score) without subsequent improvement of more than 5 points, will also be studied. Patients alive or deceased without a score decrease of more than 5 points will be censored at the point date or the date of last news if earlier. For these last three criteria, patients who did not have a quality of life questionnaire at inclusion will be excluded (their number and percentage will be given).

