3.2. SAE Reporting Procedure for Investigators to Sponsor

The Investigator must report all SAE, regardless of presumed causal relationship, to the Promotor by fax on a Serious Adverse Event form within 24 hours of learning of the event. Details of the relevant fax number for SAE will be provided as a separate document.

Information on Serious Adverse Events

Adverse Events (SAE) will be recorded on a specific Non Carbon Repeat (NCR) SAE form. Blank copies are included in the trial Investigator's File. The Investigator should follow up the event until resolution or stabilisation of the condition. Follow-up reports (as many as required) should be completed and faxed following the same procedure above.

A final report is required in any case once the condition is resolved or stabilised and no more information about the event is expected. The final report should be completed and faxed following the same procedure above.

4. Adverse Event Reporting Period

All AE that occur during the treatment period i.e. from the date of written informed consent to the final trial visit will be recorded in the CRF. In addition, any known untoward event that occurs subsequent to the AE reporting period that the Investigator assesses as possibly, probably or highly probably related to the Investigational Medicinal Product should also be reported as an AE.

XIX. QUALITY OF LIFE

Quality of life (QOL) will be measured by the general thirty-question EORTC quality of life questionnaire QLQ-C30. QOL is measured at baseline and every 3 months the first year (treatment period) and every 6 months the second year. Patients who withdraw will have a QOL assessment at discontinuation. These discontinuation data will be listed, but will not be included in tables or analyses. Every effort must be made to complete the QOL questionnaire. Where a whole questionnaire has not been completed but the patient has survived to the appropriate time, one of the following options will be recorded on the CRF.

- 1 = patient felt too ill
- 2 = clinician or nurse felt the patient was too ill
- 3 = patient felt it was inconvenient, takes too much time
- 4 = patient felt it was a violation of privacy
- 5 = patient didn't understand the actual language/ illiterate
- 6 = administrative failure to distribute the questionnaire to the patient
- 7 = other, please specify

For codes 1 or 2, data will be regarded as 'missing too ill' whereas for any of the other

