7.2.4 Transition from Phase II to Phase III

In case of transition to phase III, only results concerning the primary endpoint, safety data, and control rates during each TACE will be reported for la phase II

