8.6.2 Quality of life

- Each of the dimensions will be described at inclusion and at the end of follow-up; in addition, for each dimension, the difference between the score at inclusion and the score at the last visit will be described.
- The time without definite deterioration for each of these scores will be described by a survival curve with 95% confidence intervals.

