8.7 Criteria common to la Phase II and la Phase III

These endpoints will only be studied in la Phase II if la Phase III not occur. Comparisons between arms will only be made in Phase III.

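### SAP 5.7.4 defines worsening of the QLQ-C30 Fatigue symptom score as a score decrease, so a patient whose fatigue score only rises is never counted as progressed

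*SAP*

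**What the plan says.** SAP 5.7.4 divides the 15 QLQ-C30 scores into five functional scores, a global score, a financial problems score and "8 symptom scores (fatigue, nausea/vomiting, pain, dyspnea, sleep disturbance, loss of appetite, constipation, diarrhea". Fatigue therefore belongs to the symptom group.

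The same section then introduces a longitudinal analysis "For the QLQ-C30 Global Health, Physical Ability, Cognitive Ability, and Fatigue scores", together with three FACT scores. All seven share one definition of symptomatic progression: the "percentage of patients who had a score decrease of at least 5 points from inclusion without subsequent improvement". The next sentence extends it to dropouts: "Patients lost to follow-up without a decrease in score of at least 5 points from inclusion will be considered without symptomatic progression".

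Neither document says that Fatigue is reversed before analysis or that the direction of worsening depends on the type of scale. SAP 8.6.2 adds no direction either.

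**The concern.** One direction cannot suit both a functional score and a symptom score unless one of them is recoded. For Global Health, Physical Ability and Cognitive Ability a decrease is naturally a worsening. For a symptom score, on the ordinary meaning of the term, worsening is an increase. A rule that looks only for decreases then misses lasting worsening of fatigue and may report lasting relief as progression.

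Fatigue is the first item in the protocol's list of expected toxicities (Section X), and it is the only QLQ-C30 symptom score that the SAP selects for this percentage. Read literally, the result could show fewer progressions in an arm where fatigue worsened.

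**Working it through.** The plan gives no figure that depends on this rule, so there is nothing to reproduce. The check applies the rule as written to possible sequences of scores.

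**Inputs**
- Scale type of Fatigue: symptom score (SAP 5.7.4).
- Event: decrease of at least 5 points from inclusion, without subsequent improvement (SAP 5.7.4).
- Schedule: "QOL is measured at baseline and every 3 months the first year (treatment period) and every 6 months the second year" (Protocol XIX). This gives 4 + 2 = 6 post-inclusion questionnaires, at months 3, 6, 9, 12, 18 and 24.
- Assumption: a higher Fatigue score is worse. This is inferred from the SAP's label.
- The SAP does not define improvement for this percentage, so two readings are tried: a later rise in the score (rebound) and a later fall in the score (less fatigue).

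**Counting patterns.** Code each questionnaire as a fall of at least 5, no change, or a rise of at least 5 from inclusion.
- All patterns: 3^6 = 729.
- Patterns with no fall: 2^6 = 64. Removing the all-unchanged pattern leaves 64 − 1 = 63 with at least one rise and no fall.

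| Patterns | Written rule | Direction-corrected rule |
|---|---|---|
| Rise, no fall (63) | 0 counted, either reading | not needed for the point |
| Rise and hold, onset at questionnaire 1 to 6 (6) | 0 counted, either reading | 6 counted |
| Fall and hold, onset at questionnaire 1 to 6 (6) | 6 counted, rebound reading | 0 counted |
| Fall first seen at questionnaire 6 (1 of the row above) | counted, either reading | not counted |

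The last row holds under both readings because no later questionnaire can show an improvement.

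**Second check with scores.** Take a 0–100 grid in steps of 10, an inclusion value and three follow-ups (an illustrative grid, not from the documents). With m grid levels at or above the inclusion value, the trajectories that never fall below inclusion and end above it number m²(m − 1). Summed over m = 1 to 11, this is 4356 − 506 = 3850. The written rule counts 0 of them. Two examples:
- Fatigue 30, 50, 60, 60: not progressed as written; progressed with the direction corrected.
- Fatigue 60, 40, 30, 30: progressed as written (rebound reading); not progressed with the direction corrected.

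**Dropouts.** A patient whose fatigue rises and who is then lost has had no decrease, so the lost-to-follow-up sentence classes that patient as free of symptomatic progression.

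**The case against.** The strongest objection is that neither document states the scoring direction. Symptom score is a class label, and if Fatigue were recoded so that higher is better, the rule would work. This stands as a limit on certainty. It does not rescue the text: in that case the SAP omits a recoding step without which the rule cannot be applied correctly, and the remedy is still a sentence in the same place.

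The SAP also reads as a translation, and decrease may be loose wording for deterioration. That is possible. But programs are written from the text, and SAP 9.2.3 requires double programming only for the main criterion. Two programmers following the text would in any case agree on the same inverted result.

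The pattern counts partly restate the logic: a sequence without a decrease contains no decrease. That is fair, and they say nothing about how many patients would be misclassified. The claim must also be confined to scores that only rise. A fall followed by a lasting rise above inclusion would be counted as progression if improvement means a later fall in the score.

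Finally, the consequences are small. Fatigue remains visible elsewhere: SAP 5.7.4 has the scores described during follow-up, SAP 8.6.2 says that "for each dimension, the difference between the score at inclusion and the score at the last visit will be described", and SAP 8.6.1.3 tabulates toxicities by grade and type. SAP 8.6.2 does not list the progression percentage, and no between-arm test of it is specified. SAP 5.7.7 rules out arm comparisons of these criteria if only phase II is done, and SAP 8.7 says of the common criteria: "Comparisons between arms will only be made in Phase III". On transition, "only results concerning the primary endpoint, safety data, and control rates during each TACE will be reported for la phase II" (SAP 7.2.4). All of this stands and sets the weight of the point.

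**Conclusion.** The concern holds. As written, the symptomatic-progression percentage for Fatigue cannot count a patient whose score only rises, under either reading of improvement. Under the rebound reading it also counts lasting relief as progression. One of seven named scores is affected. The number of patients misclassified cannot be estimated from the documents.

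The conclusion rests on one inference: that a higher score on what the SAP calls a symptom score means more of the symptom, with no unstated recoding.

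The other six scores are not in question; the FACT scores are composites that the SAP does not class as symptom scores. The time to definite deterioration in SAP 5.7.4 does not list Fatigue. Protocol XIX and SAP 8.6.2 do not say which scores their deterioration analysis covers, so no error is claimed there. This is a definite wording fault in a secondary, descriptive result, and it should be corrected. No primary endpoint, sample size, alpha or phase II/III decision is affected.

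**What to change.** In SAP 5.7.4, define symptomatic progression for Fatigue as an increase of at least 5 points from inclusion without a subsequent decrease. Alternatively, state that Fatigue is reverse-coded before the common rule is applied. Change the lost-to-follow-up sentence to match, and keep the decrease rule for the other six scores. If the time-to-deterioration analysis in Protocol XIX or SAP 8.6.2 is applied to any symptom score, set its direction by scale type in the same way.

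The cost is one or two sentences, made before the database freeze as SAP 7.3 requires. No new data are needed, and sample size and timing do not change.

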5.7.7 Management of criteria between la phase II and la phase III

The common criteria for la phase II and la phase III (Section 5.7.2 and 5.7.4.) will be reviewed at the end of la phase III, or at the end of la phase II if la phase III is not performed. If these criteria are only assessed in la phase II, there will be no comparison made between arms.

In order not to introduce operational bias, all criteria can be described in la phase II (common or not to la phase III), but the common criteria must remain confidential.

In all cases, a description of the TACE treatment and a description of the catch-up treatments will be made.

6 Study populations

The study focuses on patients with hepatocellular carcinoma.

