8.1.4 Missing Data Conventions

Except in the cases specified, missing data will not be replaced.

In case of partially missing data concerning dates, the following rule will be applied: when the day is missing, the day will be considered as the 15th of the month.

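### SAP 5.7.4 counts patients lost without a recorded 5-point fall as free of symptomatic progression, which lowers the reported percentage and can open a false gap between arms if such losses are unequal

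*SAP*

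**What the plan says.** SAP 5.7.4 names seven scores: QLQ-C30 global health, physical ability, cognitive ability and fatigue, and FACT-Hep TOI, FACT-G Total and FACT-Hep Total. For each, symptomatic progression is "the percentage of patients who had a score decrease of at least 5 points from inclusion without subsequent improvement". The handling of loss follows: "Patients lost to follow-up without a decrease in score of at least 5 points from inclusion will be considered without symptomatic progression". The only exclusion the section states is that "patients who did not have a quality of life questionnaire at inclusion will be excluded (their number and percentage will be given").

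For four of the seven scores (global health and the three FACT scores) the same section also defines time to definite deterioration, and there the rule differs. The sentence beginning "Patients alive or deceased without a score decrease of more than 5 points will be censored at the point date or the date of last" sets censoring at the analysis cut-off, or at the last contact where that came first.

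The general convention in SAP 8.1.4 is "Except in the cases specified, missing data will not be replaced". On comparisons, SAP 5.7.7 says "If these criteria are only assessed in la phase II, there will be no comparison made between arms", and SAP 8.7 keeps comparisons between arms for phase III.

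Protocol section XIX gives the schedule: "QOL is measured at baseline and every 3 months the first year (treatment period) and every 6 months the second year". A questionnaire is also completed at withdrawal, but "These discontinuation data will be listed, but will not be included in tables or analyses".

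**The concern.** A patient who leaves the study before any 5-point fall has an unknown outcome. The SAP records it as a good one. The neighbouring time-to-event endpoint censors the same patient, so the two summaries in one section treat one fact in two ways. For physical ability, cognitive ability and fatigue, 5.7.4 defines no censored companion at all.

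Nothing planned would reveal the effect. The SAP has no sensitivity analysis for this percentage. The repeats in Protocol XIX (10-point threshold, deaths as events) belong to its Wilcoxon and time-to-deterioration analyses. A fall first seen on the discontinuation questionnaire is kept out of the analyses, so that patient too can be recorded as not progressed. The protocol's reason codes for a missing questionnaire include the patient being too ill, so missingness related to health was foreseen.

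At stake is a by-arm percentage that mixes quality of life with retention. If retention differs between arms, the table could show an advantage that does not exist or mask a real disadvantage.

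**Working it through.** **Inputs from the documents**
- 95 patients per arm in phase III (Protocol, Study Summary).
- 5% attrition overall, not by arm (SAP 5.5.3). It reproduces: 180 / 0.95 = 189.5, rounded up to 190. It was set for the survival sample size, not for questionnaires.
- The documents give no progression rate and no loss rate by arm for this endpoint, so there is no stated result to reproduce.

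**Assumptions**
- *p*: true progression percentage, 30 to 60%.
- *L*: share lost without a recorded fall, 5 to 30%.
- Lost patients would have progressed at the same rate as the others.

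**1. All loss before any fall.** Reported = p × (1 − L), so the shortfall is p × L. With L = 5% in both arms:
- p = 30%: 0.30 × 0.95 = 28.5%, low by 1.5 points.
- p = 60%: 0.60 × 0.95 = 57.0%, low by 3.0 points.
- With the same p in both arms, the gap between arms is zero.

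**2. Unequal early loss, same p in both arms.** Gap = p × (difference in L).

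| p | 20% lost | 5% lost | False gap |
|---|---|---|---|
| 30% | 24.0% | 28.5% | 4.5 |
| 40% | 32.0% | 38.0% | 6.0 |
| 50% | 40.0% | 47.5% | 7.5 |
| 60% | 48.0% | 57.0% | 9.0 |

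At 10% v 5% the gap is 1.5 to 3.0 points.

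**3. Loss spread over 24 months.** Let progression and loss be competing exponentials with a = −ln(1 − p) and b = −ln(1 − L). Reported = a/(a + b) × [1 − (1 − p)(1 − L)].
- p = 30%, L = 20%: 0.3567/0.5798 × 0.44 = 27.1%. L = 5%: 0.3567/0.4080 × 0.335 = 29.3%. Gap 2.2 points.
- p = 60%, L = 20%: 0.9163/1.1394 × 0.68 = 54.7%. L = 5%: 0.9163/0.9676 × 0.62 = 58.7%. Gap 4.0 points.

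At 10% v 5% the gap is 0.7 to 1.3 points.

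**4. A severe case: 30% v 15% lost, all early.** With p = 50% in both arms, 0.50 × 0.70 = 35.0% and 0.50 × 0.85 = 42.5%. For a two-proportion z test with 95 per arm, SE = √(0.35 × 0.65/95 + 0.425 × 0.575/95) = 0.0705 and 0.075/0.0705 = 1.064. Rejection probability = P(Z > 1.96 − 1.064) + P(Z < −1.96 − 1.064) ≈ 0.185 + 0.001, about 19%. At 20% v 10% the figures are 40% v 45% and about 11%. If the arm losing 30% were truly worse (60% v 50%), the table would show 0.60 × 0.70 = 42.0% v 42.5%, and a 10-point difference would disappear.

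**5. Bounds.** With 50% among those retained and 20% lost, the SAP rule gives 40%, leaving lost patients out gives 50%, and counting them as progressed gives 0.40 + 0.20 = 60%.

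**6. Direction.** A patient with a recorded fall who is then lost counts as progressed, and any later recovery goes unseen. That pushes the percentage up. A simulation on the protocol's visits (months 3, 6, 9, 12, 18, 24), with assumed score changes and noise, shows the contrast at 0 / 20 / 40% nominal loss:

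| Mean decline | Type of loss | Reported percentage |
|---|---|---|
| 10 points | unrelated to score | 63.0 / 58.9 / 54.5 |
| 10 points | driven by a fall not yet recorded | 63.1 / 51.8 / 41.7 |
| 10 points | driven by a fall already recorded | 63.0 / 63.0 / 61.1 |
| none | driven by a fall already recorded | rises from 40.5 to 46.5 |

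The levels depend on the assumed values. What matters is that the effect shrinks, and can reverse, when loss mostly follows a recorded fall.

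**The case against.** The case for leaving the rule alone has several parts.

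- **The missing-data convention.** A reader might infer that 5.7.4 breaches SAP 8.1.4. It does not: 8.1.4 allows specified exceptions and this is one. What remains is that an exception was chosen in the favourable direction and no reason is given.
- **Direction.** A reader might infer that the arm with more loss always looks better. The rule covers only patients lost without a recorded fall, and step 6 shows that other loss can cancel or reverse the effect. This stands.
- **Size.** The only attrition figure is 5%, and at 5% in both arms there is no false gap. Nothing in the documents supports 30% v 15%. At 10% v 5% early loss and 50% true progression, the same test would reject only about 6% of the time. This stands, although questionnaire loss may well exceed survival attrition.
- **The test.** SAP 8.6.2 names no test for quality of life and does not list this percentage. A test could come only from the protocol's general sentence on chi-square and Fisher tests, and only in phase III. The 19% is therefore an illustration, not a property of the plan.
- **Which arm.** A reader might assume that sunitinib patients would be lost more often because of toxicity. The documents do not establish this. Protocol XV has patients stopped for non-compliance followed further, while the toxicity table in Protocol X speaks of withdrawal from the study.
- **An alternative exists.** Time to definite deterioration is censored, but 5.7.4 defines it for only four of the seven scores, and that censoring may itself be informative.

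None of this gives a reason to record an unknown outcome as a favourable one.

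**Conclusion.** The point holds in a limited form. The percentage in SAP 5.7.4 is biased downwards by losses without a recorded fall, no other passage corrects it, and unequal loss of that kind favours the arm with more of it. The net direction in the trial cannot be known in advance.

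Size depends wholly on loss rates that the documents do not give. At the planned 5% it is small, and it falls equally on both arms if loss and true rates are equal. It becomes material for interpretation at differences such as 20% v 5%. All these figures assume that lost patients progress at the same rate as the rest; the larger ones also place every loss before any fall.

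The endpoint is secondary and is compared only in phase III. If the trial ends at phase II, the by-arm descriptions would still carry the distortion. The change should be made, but neither the primary endpoints nor the trial's decision rules are affected.

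**What to change.** In SAP 5.7.4, replace the sentence on lost patients so that, for all seven scores, a patient lost without a recorded fall is censored at the last questionnaire. Then:

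- Report the percentage with symptomatic progression as a cumulative incidence at fixed times, with death as a competing event. The present sentence is silent on deaths, and SAP 5.5.3 expects only 40% two-year survival on placebo.
- Show the number lost and the number who died, by arm, beside each percentage.
- Add one sensitivity table counting lost patients as progressed. Censoring assumes that loss is unrelated to the unseen score, and this table shows how far the result depends on that.
- State whether the discontinuation questionnaire in Protocol XIX can count as the last one, since the protocol now keeps it out of the analyses.

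Merely deleting the sentence would leave lost patients unclassified. A percentage among those with a questionnaire at each time would be a figure for completers and survivors.

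Cost: SAP wording and one extra table, with no new data collection. The reported percentages will look less favourable.
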